### 6.1.6 Censoring

In this study we expect missing outcome data to be infrequent and every effort will be made to collect all information regarding the primary outcomes through the end of the study, even in those who have discontinued the study treatment.

The censoring date for ITT analyses will be the earliest of the following: 1) most recent date of contact where the hospitalization question was assessed for the primary composite outcome or where all elements of bleeding were assessed for the primary safety outcome, including the date of a withdrawal of consent, and 2) death date (when death is not part of the outcome). Patients without any assessment of the outcome of interest will be censored at randomization.

The censoring date for AT analyses will be the earliest of the following: 1) most recent date of contact where the hospitalization question was assessed for the primary composite outcome or where all elements of bleeding were assessed for the primary safety outcome, including the date of a withdrawal of consent, and 2) death date (when death is not part of the outcome). Patients without any assessment of the outcome of interest will be censored at study drug initiation.

The censoring date for OT analysis will be the earliest of 1) most recent date of contact where the hospitalization question was assessed for the primary composite outcome or where all elements of bleeding were assessed for the primary safety outcome, including the date of a withdrawal of consent, 2) death date (when death is not part of the outcome), and 3) 7 days after the permanent discontinuation of assigned study drug. Patients without any assessment of the outcome of interest will be censored at study drug initiation.

A sensitivity analysis with the more conservative censoring date where all elements of the primary composite outcome were assessed will be performed for all three analysis populations.

### 6.1.7 Assessment of Model Assumptions

The validity of the proportional hazards assumption made in the sensitivity analysis for the non-inferiority hypothesis of the primary efficacy outcome will be examined using a standard graphical methods such as Schoenfeld residual plots; if the assumption holds, the survival curves should be approximately parallel to each other.

An additional analytical method that includes the supremum test as implemented by using the ASSESS statement in PROC PHREG in SAS version 9.4 or higher may be utilized. A p-value of < 0.05 indicates violation of the proportional hazards assumption.

If there is evidence of non-proportionality, a time dependent covariate will be included in the model to account for this.

### 6.1.8 Determination of Sample Size

With an expected accrual time of 1 year, an assumption that 50% of the expected number of patients will be enrolled in about 5 months (40% of the total accrual time), and a minimum follow-up period of 2 years, the assumed loss to follow-up rate for the period of 2 years is 5%, which is equivalent to a loss hazard rate of 0.026 for both the test and control groups. Assuming one-sided alpha of 2.5%, an

approximate power of 90%, an equal event rate of 1.75%/pt-yr in both warfarin and apixaban arms, and an absolute NI margin of 1.75%/pt-yr, the estimated sample size is 990, therefore this study will recruit approximately 1000 patients. Refer to Section 8.2 of the study protocol for the full sample size calculation and the NI margin justification.

As noted in Table 1 showing the expected statistical power based on observed event rates with 1000 patients, the power to rule out an absolute difference of 1.75%/pt-yr or a hazard ratio of 2 is greater than 70% for all scenarios where the event rates for the warfarin and apixaban arms are less than 2.8%/pt-yr. Based on historical trials with warfarin anticoagulation and the On-X valve, the hazard rate in warfarin arm is expected to be  $\leq 2.8\%$ /pt-yr. However, recognizing the uncertainty regarding the background event rate in warfarin arm, the study is designed to have the co-primary analysis with the NI and OPC tests as described in Section 1.1.1 of this document. Also, as a sensitivity analysis, a proportional hazard regression model with a hazard ratio of 2 for the NI margin will be performed.

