### 1.2 Study Design

This is a prospective, multicenter, open-label, randomized, active controlled clinical trial to determine if patients with an On-X aortic valve, alone or as an On-X Ascending Aortic Prosthesis, can be maintained safely and effectively on apixaban. The primary outcome is a composite rate of valve thrombosis and valve-related thromboembolism, which will be used for co-primary analyses. The first co-primary analysis will determine whether apixaban is non-inferior to warfarin (INR target range 2.0 - 3.0) in patients with an On-X mechanical heart valve implanted in the aortic position. The second co-primary analysis will compare the composite rate for apixaban-treated patients to updated OPC for FDA-approved mechanical heart valves in the aortic position. Each patient will be followed for at least 2 years and each randomized arm will achieve at least 800 pt-yrs.

The study will consist of approximately 1000 patients (randomized 1:1 with approximately 500 patients in the apixaban arm and 500 patients in the warfarin arm) at a minimum of 3 sites and up to 60 sites in North America, and potentially in Europe and/or Japan, who are 18 years of age or older, at least 3 months out from an On-X aortic valve implantation, and currently managing their anticoagulation with warfarin.

Patients will be randomized to either continue warfarin or switch to apixaban. Patients randomized to apixaban will receive 5 mg twice daily (BID), or apixaban 2.5 mg BID in patients with 2 or 3 of the following characteristics:

- age  $\geq$  80 years
- weight  $\leq$  60 kilograms
- creatinine  $\geq$  1.5 mg/dL (133 micromol/L)

For patients randomized to apixaban, INR testing will be performed on the current warfarin dose with the following algorithm to initiate apixaban:

1. INR  $<$  2; stop warfarin and start apixaban

2. INR 2.0 to 3.0; hold warfarin for 2 days, start apixaban on day 3
3. INR > 3.0 to 4.0; hold warfarin for 4 days, start apixaban on day 5
4. INR > 4.0; hold warfarin for 2 days, recheck INR, refer to steps 1, 2, or 3

The procedures to be performed throughout the study are outlined in the Schedule of Activities in the study protocol (see Section 1.1 of the study protocol).

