**Table 1. Expected statistical power by event rate and statistical method with 1000 patients**

Event rate in warfarin arm (%/pt-yr)	Event rate in apixaban arm (%/pt-yr)	Hazard rate approach with a NI margin of 1.75%/pt-yr	Hazard ratio approach with a NI margin of 2.0
1.00	1.00	99.1%	33.8%
1.25	1.25	97.2%	40.6%
1.50	1.50	94.1%	47.0%
1.75	1.75	90.3%	52.9%
2.00	2.00	86.1%	58.3%
2.25	2.25	81.8%	63.3%
2.50	2.50	77.5%	67.8%
2.80	2.80	72.6%	72.5%
3.00	3.00	69.5%	75.3%
3.50	3.50	62.5%	86.0%
4.00	4.00	56.6%	100.0%
4.50	4.50	51.5%	100.0%
5.00	5.00	47.2%	100.0%

The empirical type I error rate and power were evaluated using Markov chain Monte Carlo simulations with 10,000 iterations per scenario as presented in Table 2. The hypothesis statements are as follows:

$$H_0: \lambda_{\text{apixaban}} - \lambda_{\text{warfarin}} \geq 1.75\%/\text{pt-yr}$$

$$H_A: \lambda_{\text{apixaban}} - \lambda_{\text{warfarin}} < 1.75\%/\text{pt-yr},$$

where  $\lambda$  is the hazard rate of the primary efficacy outcome. The type I error rate was calculated as a proportion of rejecting the null hypothesis, i.e., how many times the upper bound of the 95% CI of hazard rate difference is less than the NI margin of 1.75%/pt-yr, when simulated 10,000 iterations under the null hypothesis ( $\lambda_{\text{apixaban}}=1.75\%/\text{pt-yr}$  and  $\lambda_{\text{warfarin}}=3.50\%/\text{pt-yr}$ ). The empirical power was calculated in the same way when simulated 10,000 iterations under the alternative hypothesis ( $\lambda_{\text{apixaban}}=1.75\%/\text{pt-yr}$  and  $\lambda_{\text{warfarin}}=1.75\%/\text{pt-yr}$ ).

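### SAP 6.1.8 claims more than 70% power to rule out a hazard ratio of 2 at all event rates below 2.8%/pt-yr, but its own Table 1 prints 33.8% to 67.8% in those rows

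*Combined protocol and SAP*

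**What the plan says.** SAP v1.4, section 6.1.8, sizes the trial on the absolute scale: "Assuming one-sided alpha of 2.5"% with "approximate power of 90%, an equal event rate of 1.75%/pt-yr in both warfarin and apixaban arms" and "an absolute NI margin of 1.75%/pt-yr", so that "the estimated sample size is 990, therefore this study will recruit approximately 1000 patients". It then cites Table 1 for a wider statement: "the power to rule out an absolute difference of 1.75%/pt-yr or a hazard ratio of 2 is greater than 70% for all scenarios" in which both arms' rates lie below 2.8%/pt-yr. The next sentence gives 2.8%/pt-yr as the highest warfarin rate expected from the historical trials. The section then acknowledges that the background rate is uncertain. It answers first with the two co-primary tests, and adds as a sensitivity analysis that "a proportional hazard regression model with a hazard ratio of 2 for the NI margin will be performed".

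Table 1 has one power column for the absolute margin and one headed "Hazard ratio approach with a NI margin of 2.0". Section 6.1.4 of the original SAP carries the same sentence and the same table.

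**The concern.** The sentence names two margins and gives one lower limit for power. In the rows it covers, the column for the absolute difference is always above 70% and the column for the hazard ratio is always below it.

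The hazard-ratio model is one of three planned sensitivity analyses of non-inferiority (SAP v1.4, section 6.8), and section 6.1.8 mentions it in the context of an uncertain background rate. A reader who trusts the sentence would expect the check to succeed in at least seven of ten trials when the drugs are equivalent. At the planning rate Table 1 implies a pass in just over five of ten. Such a reader could mistake a failure that reflects few events for evidence against apixaban.

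**Working it through.** **Inputs (SAP v1.4, 6.1.8 and 1.2).** One-sided alpha 0.025; 1000 patients, "randomized 1:1 with approximately 500 patients in the apixaban arm and 500 patients in the warfarin arm"; accrual over 1 year with half enrolled by 40% of that time; minimum follow-up 2 years; 5% loss over 2 years, so loss hazard η = −ln(0.95)/2 = 0.0256 (the SAP rounds to 0.026); equal true rates λ in both arms.

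**Step 1: reproduce the absolute-difference column and the sample size.** Let P be the probability that a patient has an observed event:

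P = λ/(λ+η) × (1 − E[exp(−(λ+η)(3 − t))])

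Here t is entry time, truncated exponential on 0 to 1 year with rate 0.822, which puts half of entries before 0.4 year. At λ = 0.0175, P = 0.0425.

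- Power = Φ(0.0175/√(2λ²/(500P)) − 1.96) = Φ(0.0175/0.00537 − 1.96) = Φ(1.30) = 90.3%, as printed.
- Patients per arm = (2λ²/P) × ((1.96 + 1.2816)/0.0175)² = 494.4, rounded up to 495, so 990 in total, as printed.

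All 13 rows of this column reproduce to within 0.1 percentage point.

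**Step 2: reproduce the hazard-ratio column.** With D total events, a true hazard ratio of 1 and 1:1 allocation (Schoenfeld):

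Power = Φ(ln 2 × √D/2 − 1.96)

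The printed values from 1.00 to 3.00%/pt-yr are matched to within 0.1 point by D = 1000 × (1 − exp(−2λ)), that is, two years per patient and no loss. The SAP does not state this basis; I infer it from the fit. At 1.75%: D = 1000 × (1 − exp(−0.035)) = 34.4, and power = Φ(0.6931 × 5.864/2 − 1.96) = Φ(0.072) = 52.9%.

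**Step 3: put the hazard ratio on the planned follow-up.** Use D = 1000 × P, with P from step 1. At 1.75%: D = 42.5, and power = Φ(0.6931 × 6.520/2 − 1.96) = Φ(0.30) = 62%.

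| Rate (%/pt-yr) | Difference, printed | HR 2, printed | HR 2, two-year formula | HR 2, planned follow-up |
|---|---|---|---|---|
| 1.00 | 99.1% | 33.8% | 33.8% | 40% |
| 1.25 | 97.2% | 40.6% | 40.6% | 48% |
| 1.50 | 94.1% | 47.0% | 47.0% | 55% |
| 1.75 | 90.3% | 52.9% | 52.9% | 62% |
| 2.00 | 86.1% | 58.3% | 58.3% | 67% |
| 2.25 | 81.8% | 63.3% | 63.3% | 72% |
| 2.50 | 77.5% | 67.8% | 67.7% | 77% |
| 2.80 | 72.6% | 72.5% | 72.5% | 81% |

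A simulation of 10,000 trials per rate on the planned follow-up, comparing the upper 95% bound of the log rate ratio with ln 2, gave 61.0% at 1.75% and 39.9% to 75.3% over the first seven rows. No variant tried lifts all seven rows above 70%.

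**Step 4: where 70% is reached.** D = 4 × ((1.96 + 0.524)/0.6931)² = 51.4 events. On the two-year basis, 1 − exp(−2λ) = 0.0514 gives λ = 2.64%/pt-yr. On the planned follow-up, P = 0.0514 gives λ = 2.13%/pt-yr.

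**Step 5: failure with identical drugs at 1.75%.** 100 − 52.9 = about 47% by Table 1; 100 − 62 = about 38% on planned follow-up.

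**The case against.** The best defence is that *or* means at least one of the two approaches exceeds 70%. That is literally true below 2.8%. The limit also has a source of its own: it is the expected maximum warfarin rate, close to the pooled upper confidence bound of 2.81%/pt-yr in protocol section 8.2, and the two columns cross there (72.6% and 72.5%). So this reading cannot be excluded. It is still unnatural, because on that reading the claim holds in every row of Table 1, above the limit as well as below. The printed hazard-ratio power at 3.00% and higher is 75.3% or more. The entries from 3.50% upward depart from the two-year formula, but the formula itself gives 81.3% to 92.2% there. The absolute-difference column, by contrast, does drop below 70% just past the limit, to 69.5% at 3.00%. At best the sentence is ambiguous, and it needs rewording either way.

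The second defence is that little depends on it, and most of that stands. The correct figures are printed directly below the sentence. The hazard-ratio model is a labelled sensitivity analysis, and success is declared on the two co-primary tests alone (section 6.3.1). Nothing in the documents says how a failed hazard-ratio check will be read, so over-reading is a possibility and not a planned step.

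Third, the printed column understates the check on the planned follow-up: the 2.25% and 2.50% rows then exceed 70%. The statement is contradicted in all seven rows only against the printed figures; on planned follow-up it fails in five, from 1.00% to 2.00%.

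Finally, SAP v1.4, section 6.1.3, records that the trial was stopped on safety grounds. Prospective power no longer governs conduct, and planned follow-up is not achieved follow-up.

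**Conclusion.** On its natural reading, the 70% statement is right for the absolute difference and wrong for the hazard ratio. Against Table 1 the hazard-ratio power is 33.8% to 67.8% for rates from 1.00 to 2.50%/pt-yr, and 52.9% at the planning rate. On planned accrual, follow-up and loss it is about 40% to 77%, and about 62% at the planning rate. These figures assume constant hazards, equal true rates and the Schoenfeld approximation; the two-year basis of the printed column is inferred.

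This is a reporting error of modest consequence. A reader might infer that the trial is underpowered for its primary question. The documents do not support that: the primary margin is absolute, and both the 990 patients and the 90% power reproduce. A reader might also infer that a failed hazard-ratio check will be taken as evidence against apixaban. The documents support only that it could be. Early stopping may have lowered the achieved power further, but the documents give no event counts from which to say by how much.

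**What to change.** In section 6.1.8, limit the statement of more than 70% power to the absolute difference of 1.75%/pt-yr. Then give the hazard-ratio power in its own sentence: 33.8% to 67.8% for rates of 1.00 to 2.50%/pt-yr and 52.9% at 1.75% by Table 1, if the authors confirm the two-year, no-loss basis; or about 40% to 77%, and about 62% at 1.75%, on the planned accrual, follow-up and loss. State which basis is used, and preferably put both columns on the same one. If a threshold is quoted, 70% is reached at about 2.6%/pt-yr on the two-year basis and about 2.1%/pt-yr on planned follow-up.

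Do not add a rule for discounting a failed hazard-ratio check. That would go beyond correcting the figure, and after the trial has stopped it would look like a late decision to set aside an unfavourable result.

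The cost is a change of wording in the SAP and a less favourable stated power for one sensitivity analysis. No design element, margin or primary analysis changes.

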**Table 1. Expected statistical power by event rate and statistical method with 1000 patients**

Event rate in warfarin arm (%/pt-yr)	Event rate in apixaban arm (%/pt-yr)	Hazard rate approach with a NI margin of 1.75%/pt-yr	Hazard ratio approach with a NI margin of 2.0
1.00	1.00	99.1%	33.8%
1.25	1.25	97.2%	40.6%
1.50	1.50	94.1%	47.0%
1.75	1.75	90.3%	52.9%
2.00	2.00	86.1%	58.3%
2.25	2.25	81.8%	63.3%
2.50	2.50	77.5%	67.8%
2.80	2.80	72.6%	72.5%
3.00	3.00	69.5%	75.3%
3.50	3.50	62.5%	86.0%
4.00	4.00	56.6%	100.0%
4.50	4.50	51.5%	100.0%
5.00	5.00	47.2%	100.0%

The empirical type I error rate and power were evaluated using Markov chain Monte Carlo simulations with 10,000 iterations per scenario as presented in Table 2. The hypothesis statements are as follows:

$$H_0: \lambda_{\text{apixaban}} - \lambda_{\text{warfarin}} \geq 1.75\%/\text{pt-yr}$$

$$H_A: \lambda_{\text{apixaban}} - \lambda_{\text{warfarin}} < 1.75\%/\text{pt-yr},$$

where  $\lambda$  is the hazard rate of the primary efficacy outcome. The type I error rate was calculated as a proportion of rejecting the null hypothesis, i.e., how many times the upper bound of the 95% CI of hazard rate difference is less than the NI margin of 1.75%/pt-yr, when simulated 10,000 iterations under the null hypothesis ( $\lambda_{\text{apixaban}}=1.75\%/\text{pt-yr}$  and  $\lambda_{\text{warfarin}}=3.50\%/\text{pt-yr}$ ). The empirical power was calculated in the same way when simulated 10,000 iterations under the alternative hypothesis ( $\lambda_{\text{apixaban}}=1.75\%/\text{pt-yr}$  and  $\lambda_{\text{warfarin}}=1.75\%/\text{pt-yr}$ ).

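### SAP Table 1: the last four hazard-ratio powers (86.0% and three entries of 100.0%) are wrong, and the column rests on a shorter follow-up than the one beside it

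*Combined protocol and SAP*

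**What the plan says.** Section 6.1.8 of SAP v1.4 sets the design inputs once. They are 1000 patients, "randomized 1:1 with approximately 500 patients in the apixaban arm and 500 patients in the warfarin arm" (Section 1.2), one-sided alpha 2.5%, an accrual time of 1 year in which "50% of the expected number of patients will be enrolled in about 5 months (40% of the total accrual time"), "a minimum follow-up period of 2 years", and a loss hazard of 0.026 per year.

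Table 1, titled "Expected statistical power by event rate and statistical method with 1000 patients", then shows two power columns for equal rates in both arms: "Hazard rate approach with a NI margin of 1.75%/pt-yr" and "Hazard ratio approach with a NI margin of 2.0". No separate follow-up assumption is given for either. The hazard-ratio column climbs from 33.8% at 1.00%/pt-yr to 75.3% at 3.00, then prints 86.0% at 3.50 and 100.0% at 4.00, 4.50 and 5.00.

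The text reads the table as showing that "the power to rule out an absolute difference of 1.75%/pt-yr or a hazard ratio of 2 is greater than 70" per cent whenever both rates are below 2.8%/pt-yr. It then acknowledges uncertainty about the warfarin rate, points to the co-primary non-inferiority and OPC tests, and adds the Cox analysis with margin 2 as a sensitivity analysis. SAP v1.0, Section 6.1.4, carries the same table values.

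**The concern.** The jump in the column is implausible on its face. Power rises by 2.8 points from 2.80 to 3.00%/pt-yr, then by 10.7 points to 3.50, then by 14 points to certainty at 4.00. No time-to-event test on roughly 100 events can rule out a hazard ratio of 2 with power that rounds to 100.0%. The two columns also sit under one heading as if they were directly comparable.

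Table 1 is where a reader learns how each analysis would behave if the warfarin rate differs from 1.75%/pt-yr. As printed, it says the hazard-ratio analysis has about even odds at the planning rate and cannot fail at 4%/pt-yr or more. If both statements are wrong, the two approaches cannot be weighed from this table.

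**Working it through.** **Inputs (SAP v1.4, Section 6.1.8).** N = 1000 at 1:1; one-sided alpha 0.025 (z = 1.96); true hazard ratio 1 in every row; margins of hazard ratio 2 and 0.0175 per pt-yr; accrual over 1 year; follow-up of 2 to 3 years by entry date; loss hazard 0.026 (check: −ln(0.95)/2 = 0.0256). Entry is modelled as a truncated exponential with half the patients in by 0.4 year (parameter 0.822).

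**Step 1: reproduce the absolute-margin column.** With event rate λ and entry time u, the event probability p is the average over entry times of λ/(λ+0.026) × [1 − exp(−(λ+0.026)(3−u))]. Then

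power = Φ(0.0175 / √(2λ²/(500p)) − 1.96).

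At λ = 0.0175, p = 0.0425, which is 21.2 events and about 1,214 pt-yr per arm. The standard error is 0.0175 × √(2/21.2) = 0.00537, so power = Φ(3.26 − 1.96) = 90.3%, as printed. All 13 rows agree within 0.1 point, and the sample size comes out at 989.2, i.e. 990. This column therefore uses the stated design.

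**Step 2: reproduce the hazard-ratio column.** The Schoenfeld formula is

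power = Φ(ln 2 × √E / 2 − 1.96), where E is the total number of events.

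The first nine rows (1.00 to 3.00) agree within 0.1 point when E = 1000 × (1 − exp(−2λ)), that is, exactly 2 years per patient and no loss. At 1.75%: E = 34.4, and Φ(0.3466 × 5.87 − 1.96) = 52.9%, as printed. That corresponds to about 983 pt-yr per arm. On the design follow-up, E = 42.5 and power is Φ(0.3466 × 6.52 − 1.96) = 61.8%. As a cross-check, putting the flat 2 years into the absolute-margin formula gives 83.5% at 1.75%, not the printed 90.3%, so the two columns do not share a basis.

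**Step 3: all rows on both bases.**

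| Rate (%/pt-yr) | Printed (%) | Events, flat 2 y | Power, flat 2 y (%) | Events, design | Power, design (%) |
|---|---|---|---|---|---|
| 1.00 | 33.8 | 19.8 | 33.8 | 24.5 | 40.4 |
| 1.25 | 40.6 | 24.7 | 40.6 | 30.5 | 48.2 |
| 1.50 | 47.0 | 29.6 | 47.0 | 36.5 | 55.4 |
| 1.75 | 52.9 | 34.4 | 52.9 | 42.5 | 61.8 |
| 2.00 | 58.3 | 39.2 | 58.3 | 48.4 | 67.4 |
| 2.25 | 63.3 | 44.0 | 63.3 | 54.3 | 72.4 |
| 2.50 | 67.8 | 48.8 | 67.7 | 60.1 | 76.6 |
| 2.80 | 72.5 | 54.5 | 72.5 | 67.1 | 81.0 |
| 3.00 | 75.3 | 58.2 | 75.3 | 71.7 | 83.5 |
| 3.50 | **86.0** | 67.6 | 81.3 | 83.1 | 88.5 |
| 4.00 | **100.0** | 76.9 | 86.0 | 94.4 | 92.0 |
| 4.50 | **100.0** | 86.1 | 89.5 | 105.5 | 94.5 |
| 5.00 | **100.0** | 95.2 | 92.2 | 116.5 | 96.3 |

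The last four printed values match neither basis. The 86.0% at 3.50 equals the flat 2-year value for 4.00, which suggests an entry placed one row too high.

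**Step 4: could 100.0% be right on any basis?** To print as 100.0%, power must reach 99.95%, which needs E = 4 × (1.96 + 3.29)² / (ln 2)² ≈ 230 events. With every patient followed for 3 full years and no loss, a rate of 5%/pt-yr gives 139 events and 98.3% (99.3% at one-sided 0.05).

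**Step 5: check by simulation.** Cox/Wald simulation on the design follow-up (5,000 runs per scenario) gave 60.9% at 1.75, 82.2% at 3.00, and 87.5, 91.8, 93.7 and 95.5% at 3.50 to 5.00. These are within about 1.5 points of the Schoenfeld values.

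**Step 6: where the two approaches cross.** The printed columns meet at 2.80%/pt-yr (72.6 and 72.5%). On the common design basis they meet at about 2.5%/pt-yr (77.5 and 76.6% at 2.50).

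**The case against.** The three 100.0% entries cannot be defended, and they stand identically in both SAP versions, so they are not an extraction artefact. The fair objections concern scope and weight.

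- **The 2-year basis is inferred, not stated.** This stands. Nine rows agreeing within 0.1 point make the inference strong. If it is right, the guaranteed minimum follow-up was used, which understates power and could be called conservative. It is still unlabelled and differs from the adjacent column.
- **The size depends on the benchmark.** This stands. The largest overstatement is 14 points on the column's own 2-year basis (100.0 against 86.0) but 8 points on the design basis. On the design basis the 3.50 row is 2.5 points too low, not too high, and within 2 points of the simulated 87.5%.
- **The sentence that reads the table is true if it means at least one of the two approaches.** This also stands, because the absolute-margin column exceeds 70% throughout that range. The printed hazard-ratio column, however, is below 70% in all seven rows from 1.00 to 2.50.
- **The consequences are limited.** This stands. The Cox model is a sensitivity analysis, success is declared on the co-primary tests, and the four faulty rows lie above the expected ceiling of 2.8%/pt-yr. The SAP answers the rate uncertainty first with the co-primary tests. SAP v1.4, Section 6.1.3, records that the trial had already been stopped.

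These points limit the weight of the finding. None makes the printed figures correct.

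**Conclusion.** The concern holds. The last four hazard-ratio entries agree with neither the basis of the rows above them nor the stated design, and three of them are unattainable with the expected number of events.

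Measured against the design's own follow-up, the column is about 7 to 9 points too low from 1.00 to 3.00%/pt-yr, 2.5 points too low at 3.50, and about 8.0, 5.5 and 3.7 points too high at 4.00, 4.50 and 5.00. At the planning rate, power is about 62% rather than 52.9%.

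The result rests on exponential event times, truncated-exponential entry fitted to the stated 40% point, and the Schoenfeld approximation without covariate adjustment. The absolute-margin column, the sample size of 990 and the primary power are confirmed. This should be corrected, but it does not threaten the primary analysis.

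**What to change.** Recompute the hazard-ratio column with the accrual, follow-up and loss assumptions used for the absolute-margin column. Approximate values for rates 1.00 to 5.00 are 40, 48, 55, 62, 67, 72, 77, 81, 84, 88, 92, 94 and 96%. State the follow-up basis and the power formula under the table. If a flat 2-year basis is kept on purpose, label it and correct the last four rows to 81.3, 86.0, 89.5 and 92.2%.

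Reword the sentence in Section 6.1.8 to give power for each approach separately. On the design basis, the absolute-margin test exceeds 70% at every tabulated rate up to 2.80%/pt-yr, while the hazard-ratio test does so only from 2.25%/pt-yr upwards.

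The cost is one table column and one sentence. Conduct, sample size and the planned tests do not change.
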